#### Part B

Sensitivity analyses will be specified in the SAP.

#### 13.6.2. Demographic and Baseline Data

Demographic and baseline data will be summarized by treatment group and frequency distributions and summary statistics presented.

## 13.6.3. Patient Disposition

Patient disposition will be summarized and summary statistics presented.

## **13.6.4.** Efficacy

#### Part A

For the primary analysis, the cumulative number of GdE lesions from Week 12 to Week 24 will be compared between the 1 mg RPC1063 group and the placebo group using the stratified Wilcoxon-Mann-Whitney test, stratified by presence of GdE lesions at baseline (absent or present). This comparison will be assessed using a 2-sided test at the alpha=0.04944 level of significance (to keep the overall Part A level of significant at alpha=0.05, accounting for the O'Brien-Fleming adjustment and interim analysis) (Reboussin, 2000). If the comparison between the 1 mg RPC1063 group and placebo is statistically significant, then a second primary analysis will similarly compare the 0.5 mg RPC1063 group and the placebo group, also based on a 2-sided test at the alpha=0.04944 level of significance. Sensitivity and descriptive analyses will also be presented.

The secondary endpoint of the proportion of patients free of GdE lesions at Week 24 will be analyzed using a logistic regression model with treatment group (three levels) and presence of baseline GdE lesions (absent, present) as factors. Pairwise comparisons between the 1 mg RPC1063 group and placebo, and between the 0.5 mg RPC1063 group and placebo, will be tested.

Quantitative endpoints such as the percent brain volume change over 24 weeks will be analyzed using analysis of covariance models with treatment group as a factor and the baseline value of the corresponding parameter as a covariate.

Endpoints that are defined in terms of lesion counts will be analyzed using the Wilcoxon-Mann-Whitney test. These analyses will include only the two groups being compared.

All secondary endpoints will be analyzed using 2-sided tests at the 5% level of significance.

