# 8.1.3. Exploratory Study Objectives

#### Part A

## Part B

# 8.2. Endpoints

## 8.2.1. Efficacy Endpoints

#### Part A

Primary Efficacy Endpoint:

• Total number of GdE lesions, assessed on brain MRIs from Week 12 to Week 24

Key Secondary Efficacy Endpoints (rank ordered):

- The number of GdE lesions at Week 24
- Total number of new or enlarging hyperintense T2-weighted brain MRI lesions from Week 12 to Week 24
- ARR at the end of Week 24

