# 13.2. Sample Size Estimation

### Part A

The primary analyses will compare the cumulative number of new GdE lesions at the end of Week 24 in each of the RPC1063 groups to the placebo group using a 2-sided Wilcoxon-Mann-Whitney test. For this type of nonparametric analysis, the parameter of interest for sample size/power considerations is the probability that a randomly selected patient in an active treatment arm will have fewer lesions than a randomly selected patient in the placebo arm. Limited data are available from which to estimate this parameter. However, based on the use of patient-level data from Tubridy et al. (1999) and Miller et al. (2003), estimates of this probability range from 0.634 to 0.754. Using the approach of Noether (1987), a sample size of 59 patients per group will provide 80% power to detect a difference if the true value of this probability is equal to 0.65 (Noether, 1987). Assuming a dropout rate of 15%, the planned enrollment is 210 patients (70 patients per arm).

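### Part A ranks its key secondary endpoints but the protocol states no testing sequence for them, and it names no stratification for the lesion-count secondaries although the primary test is stratified

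*Protocol*

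**What the plan says.** **Ranking.** The synopsis and protocol section 8.2.1 give Part A three key secondaries under the label "Key Secondary Efficacy Endpoints (rank ordered". In order they are the GdE lesion count at Week 24, new or enlarging T2 lesions from Week 12 to Week 24, and annualized relapse rate (ARR) at Week 24.

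**Primary test (13.6.4, Part A).** The cumulative GdE count from Week 12 to Week 24 is compared with a Wilcoxon-Mann-Whitney test stratified by presence of GdE lesions at baseline. The dose order is explicit: "If the comparison between the 1 mg RPC1063 group and placebo is statistically significant, then a second primary analysis will similarly compare" 0.5 mg with placebo, "also based on a 2-sided test at the alpha=0.04944 level of significance".

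**Secondary tests (same section).**
- On level: "All secondary endpoints will be analyzed using 2-sided tests at the 5% level of significance". No sequence or gate accompanies this.
- On lesion counts: "Endpoints that are defined in terms of lesion counts will be analyzed using the Wilcoxon-Mann-Whitney test". Stratification is not mentioned.
- "The secondary endpoint of the proportion of patients free of GdE lesions at Week 24" is analysed by logistic regression with baseline GdE presence as a factor. It matches a secondary objective in 8.1.2 but is not in the 8.2.1 endpoint list.
- No method is named specifically for ARR, the third-ranked endpoint.

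**Sample size (13.2, Part A).** "The primary analyses will compare the cumulative number of new GdE lesions at the end of Week 24" in each RPC1063 group with placebo, and "a sample size of 59 patients per group will provide 80% power to detect a difference" if the true probability is 0.65.

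**SAP.** Section 2 says that Part A has its own SAP. The SAP at hand covers Part B only.

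**The concern.** A rank order among endpoints matters only if it governs testing. The protocol writes such rules elsewhere. The Part A primary gates 0.5 mg behind 1 mg, and Part B has a sequence through its key secondaries that depends on how many doses succeed on the primary. For the Part A key secondaries there is a ranking and a flat 5% level, with nothing joining them. A team following 13.6.4 literally could run all six comparisons at 5% whatever the primary shows, and report whichever succeed as key secondary findings.

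Stratification raises a related question. The section conditions on baseline GdE presence for the primary count and again for the lesion-free proportion, but names no stratification for the two lesion-count key secondaries. If baseline GdE activity predicts later lesion counts, the unstratified test gives up power that costs nothing to keep.

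Two descriptions also leave room for argument at analysis. The Week 24 GdE analysis that 13.6.4 spells out is the lesion-free proportion, while the ranked endpoint is the count. And 13.2 describes the primary endpoint differently from the rest of the protocol.

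**Working it through.** **1. The plan's own figures.** Noether's formula for two equal groups is n per group = (z_α/2 + z_power)² / [6(P − 0.5)²].
- Inputs from 13.2 and 13.6.4: P = 0.65, power 80%, two-sided α = 0.04944.
- n = 58.3, so 59 per group (58.1 at α = 0.05, also 59). 59 / 0.85 = 69.4, so 70 per arm.
- Power at 59 per group: Φ(√(6 × 59) × 0.15 − 1.965) = Φ(0.857) = 80.4%.

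The stated 59, 80% and 70 all reproduce.

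**2. Six secondary tests at 5%.** There are 3 endpoints × 2 doses. Independence would give 1 − 0.95⁶ = 26.5%. The doses share a placebo arm of equal size, so their test statistics correlate at about 0.5. The documents do not give the correlation between endpoints, so it is varied. Simulated correlated normal statistics with all six nulls true give:

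| Assumed endpoint correlation | Chance of at least one false claim |
|---|---|
| 0 | 24.8% |
| 0.3 | 23.7% |
| 0.5 | 22% |
| 0.7 | 19.2% |
| 0.8 | 17.3% |

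A fixed sequence stops at the first failure, so it holds this figure at 5% or less.

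**3. Stratified against plain Wilcoxon.** Every input except the arm size is an assumption, since the documents give no lesion-count distribution: 40% of patients with baseline GdE lesions; mean count 0.5 without them and 2 or 4 with them; negative binomial shape 0.8; rate ratio 0.35; 70 per arm; 4,000 simulated trials per scenario.

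| Mean with baseline GdE | Plain | Stratified |
|---|---|---|
| 2 | 0.80 | 0.86 |
| 4 | 0.75 | 0.89 |

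Simulation error is about √(0.8 × 0.2 / 4000) = 0.006, and a repeat of the last plain figure gave 0.74. The gain grows with the prognostic strength of baseline GdE and would vanish if there were none.

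**4. Power for 0.5 mg through the gate.** This is the probability that both primary tests succeed, by bivariate normal with correlation 0.5, 59 per group and α = 0.04944.

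| P for 1 mg | P for 0.5 mg | Gated power for 0.5 mg |
|---|---|---|
| 0.65 | 0.65 | 69.3% |
| 0.70 (assumed) | 0.65 | 79.0% |
| 0.754 (top of the range in 13.2) | 0.65 | 80.4% |

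With all 70 per arm evaluable and both doses at 0.65 it is 78.2%.

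**5. Description of the primary endpoint.** The objectives, 8.2.1, the synopsis methods and 13.6.4 all use total or cumulative GdE lesions from Week 12 to Week 24. Section 13.2 alone refers to new lesions at the end of Week 24.

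**The case against.** The strongest reply is that the governing document is missing. Section 13.3 says that a SAP will expand on the protocol's methods, and Part A has a separate one. The gate, the stratification and the ARR model may all be there. This stands as a limit. A reader might infer that key secondary claims in Part A have no error control; the documents show only that the protocol states none.

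Next, a 5% level for each test is compatible with a fixed sequence, which also spends the full 5% at every step. That is fair: the text is underspecified rather than self-contradictory. But nothing in 13.6.4 turns the ranking into a sequence, and the Part B text shows that the protocol spells such a rule out when it wants one.

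Third, it is tempting to call all the secondaries unstratified. The text does not support that. The lesion-free proportion is adjusted for baseline GdE, ARR is not a lesion count, and for the two lesion-count endpoints the reading rests on a contrast of wording within one section. The lesion-free proportion is not a stray endpoint either, since it is a stated secondary objective, and the Week 24 count is covered by the general sentence on lesion counts.

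Fourth, a reader might infer from the dose gate that the 80% power is overstated. It is not. It is a correct figure for one comparison, and the protocol never claims it for the sequence. The 69% holds only if both doses have P = 0.65, whereas section 9.2 expects less than maximal efficacy at the lower dose's target.

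Finally, Part A is the phase 2 portion, and the odd wording in 13.2 is isolated. Both are true. They lower the stakes but do not remove the ambiguity.

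**Conclusion.** The point holds for the protocol text. The Part A key secondaries carry a ranking that no stated rule uses. Read literally, six tests at 5% give a 17% to 25% chance of at least one false claim when all six nulls are true, assuming a between-dose correlation of 0.5 and endpoint correlations from 0.8 down to 0. The two lesion-count key secondaries are assigned a Wilcoxon test without the stratification used for the primary. Under the assumed count distribution that costs about 6 to 14 percentage points of power; the direction is more secure than the size.

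The dose order for the primary is carried through properly, and the sample size is right. The remaining items, on which Week 24 GdE analysis is ranked and on the endpoint wording in 13.2, are clarifications. None of this shows what the Part A SAP says. If that SAP already contains a gate and a stratified test, what remains is to bring the protocol text into line.

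**What to change.** In 13.6.4, Part A:
- Test the key secondaries in the listed order, 1 mg then 0.5 mg within each endpoint, each only after the preceding test and that dose's primary test have succeeded.
- Say what happens if 1 mg succeeds and 0.5 mg fails on the primary. Read strictly, the sequence ends there. Carrying on with 1 mg at 5% would allow up to 1 − (1 − 0.04944)(1 − 0.05) = 9.7% if both nulls were true and the two tests independent.
- Use the primary's baseline-GdE-stratified Wilcoxon test for the lesion-count secondaries.
- Make the Week 24 GdE count the ranked test and the lesion-free proportion supportive. Name the ARR method.

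In 13.2, Part A, describe the primary endpoint as total GdE lesions from Week 12 to Week 24. Leave the 80% as it is. At most, add that power for 0.5 mg through the gate is about 69% if both doses have P = 0.65, rising to about 80% if the 1 mg effect is larger.

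The cost is protocol wording, with matching text in the Part A SAP if it differs, and no added patients. The real price is that an early failure in the sequence closes off later secondary claims.

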#### Part B

The primary analysis for the ARR will be carried out using a Poisson regression model. The model will compare treatment groups, adjusted for region, age, and the number of GdE lesions at baseline. To account for multiple comparisons, each of the 2 treatment comparisons with IFN  $\beta$ -1a will be tested at the alpha = 0.025 level. Results will be summarized by randomized treatment group and expressed as unadjusted and adjusted relapse rates, odds ratios, corresponding 95% confidence intervals, and p-values.

The relapse rate will be based on only those relapses that were determined by the treating investigator to meet the protocol-defined definition of relapse, based on the EDSS scores obtained by the blinded evaluator (Section 9.1.2.3). New or recurrent neurological symptoms that occur less than 30 days following the onset of a protocol-defined relapse will be considered part of the same relapse, i.e., if 2 relapses have onset days that are  $\leq$ 30 days of one another, they will be counted as 1 relapse (see Section 9.1.2.3).

The relapse rate for each treatment group will be calculated as:

(total relapses in the arm) / (total days in the study for the arm) \* 365.25

The 3 key secondary endpoints will be tested in order in the RPC1063 1 mg dose above the RPC1063 0.5 mg dose. If both doses are significant on the primary endpoint, then the first comparison on the key secondary endpoints will be between the RPC1063 1 mg group and the IFN  $\beta$ -1a group at the 5% level of significance. If that comparison is successful, then the same endpoint will be tested for the RPC1063 0.5 mg group vs. the IFN  $\beta$ -1a group comparison at the 5% level of significance. This procedure will continue down the key secondary endpoint list until a comparison fails to reach statistical significance,

the primary endpoint, then the will be employed on the surviving dose only, at the 2.5% level of significance for each key secondary endpoint.

The key secondary endpoints of cumulative number of new or enlarging T2 lesions between baseline and Month 12 and the number of GdE lesions at Month 12 will be analyzed using a negative binomial regression model with factors for treatment, region, age, and baseline number of GdE lesions. The key secondary endpoint of time to onset of disability progression will be compared between treatment groups using Kaplan-Meier estimation and a Cox proportional-hazards model adjusted for region, age, and baseline EDSS score. Results will be summarized by randomized treatment group and expressed as proportions, corresponding 95% confidence intervals, and p-values. Disability progressions confirmed at 3 months and at 6 months will be analyzed separately.

Other secondary endpoints that are defined as continuous variables will be analyzed using analysis of covariance models adjusted for region, age, and baseline measurements of the response parameter of interest. Other secondary endpoints defined as response proportions will be analyzed using a Cochran-Mantel-Haenszel test stratified by region and baseline EDSS category.

#### 13.6.5. Pharmacokinetics

Population PK analyses will use the RPC1063 dose-concentration-time data from this study combined with data from other Phase 2 and Phase 3 studies to assess the influence of study patient covariates on the exposure of RPC1063.

#### **13.6.6.** Safety

The incidence of treatment-emergent AEs will be summarized for each treatment group overall, by severity, and by relationship to study drug. SAEs will be presented by treatment group and by relationship to study drug. Summary tables will present incidence estimates and individual event rates by system organ class as well as within each system organ class. Patients experiencing an event more than once with varying severity will be counted only once with the maximum severity within each system organ class/preferred term. For incidence of relationship to study drug, patients will be counted only once, in the category of the strongest relationship to study drug within each system organ class/preferred term.

## 13.6.7. Interim Analysis

An interim analysis of Part A will be completed approximately 1 month prior to completion of Part A enrollment. At this time point, it is estimated that approximately 80-90% of patients will have received treatment and approximately 45% of patients will have completed 12 weeks of treatment. The primary purpose of the interim analysis is to summarize safety endpoints and to provide a preliminary assessment of the primary efficacy endpoint. The efficacy endpoint for the interim analysis will be the number of GdE lesions using all data from patients who provide data through at least Week 12 (appropriately scaled). Based on the Lan-DeMets method for group sequential trials using O'Brien-Fleming boundaries (Reboussin, 2000), the significance levels at the interim and final analyses will be 0.00167 and 0.04944, respectively.

#### 13.6.8. Data Monitoring Committee (DMC)

An independent DMC will be charged with monitoring accumulating data from the trial, as well as general aspects of trial conduct.

The committee will meet periodically during the study to review aggregate analyses by treatment group concerning enrollment, treatment compliance, adherence to follow-up schedule, and safety data from the trial. The DMC may recommend modifying or stopping the trial early due to safety concerns based on data reviews, including the interim analysis of Part A.

The blinding plan to assure that all personnel at Receptos and all personnel involved in the conduct of the study remain blinded to the results of interim reviews will be specified in the DMC Charter.

## 14. MONITORING PROCEDURES (QUALITY ASSURANCE)

The Sponsor has ethical, legal, and scientific obligations to conduct this study in accordance with established research principles and ICH GCP guidelines. As such, in order to fulfill these obligations and to maintain current of study progress, the Sponsor's monitors or representatives will visit the investigative sites during study conduct, in addition to maintaining telephone and written communication. On-site visits, telephone calls, and regular inspection of the eCRFs will be conducted in order to assess patient enrolment, compliance with protocol procedures, completeness and accuracy of data entered on the eCRFs, verification of eCRF data against original source documents, and occurrence of AEs. The Investigator must provide the monitor with full access to all source and study documents.

## **14.1.** Routine Monitoring

Sponsor assigned monitors will conduct regular site visits to the investigational facilities for the purpose of monitoring various aspects of the study. The Investigator must agree to Sponsor-authorized personnel having direct access to the clinical (or associated) files and clinical study supplies (dispensing and storage areas) for all study patients considered for study entry for the purpose of verifying entries made in the eCRF, and assist with their activities, if requested. The Investigator will make available adequate time and space for monitoring visits.

The site must complete the eCRFs in a timely manner and on an ongoing basis to allow regular review by the Study Monitor.

Whenever a patient name is revealed on a document that is to be collected for the Sponsor the name must be blacked out permanently by the site personnel, leaving the initials visible, and annotated with the patient number as identification.

# 14.2. Inspections and Auditing Procedures

The Sponsor or its representative may conduct audits at the investigative sites including, but not limited to, drug supply, presence of required documents, the informed consent process, and comparison of eCRFs with source documents. All medical records (progress notes) must be available for audit. The Investigator agrees to participate with audits conducted at a convenient time in a reasonable manner.

Government regulatory authorities may also inspect the Investigator during or after the study. The Investigator or designee should contact the Sponsor/CRO immediately if this occurs. He/she must cooperate fully with regulatory authorities or other audits conducted at a convenient time in a reasonable manner.

The purpose of an audit is to assess whether ethics, regulatory and quality requirements are fulfilled.

#### 15. STUDY MANAGEMENT AND MATERIALS

## **15.1.** Electronic Case Report Forms

An eCRF will be used to store and transmit patient information. The file structure and format for the eCRF will be provided by the Sponsor or their representative and should be handled in accordance with the instructions provided.

The eCRF must be reviewed and electronically signed, and dated by the Investigator.

Access to the eCRF will be strictly password protected and limited to personnel directly participating in the study. Data should be entered into the eCRF completely by treating personnel or the study coordinator. The eCRF must be completed as soon as possible after any patient evaluation or communication. If data is to be changed due to erroneous input or other reason, an electronic audit trail will track these changes. The eCRFs and computers that store them must be accessible to Study Monitors and other regulatory auditors.

#### 15.2. Data Collection

During each study visit, a physician participating in the study will maintain progress notes in the patient's medical records to document all significant observations. At a minimum, these notes will contain: the date of the visit and the corresponding day or visit in the study schedule (e.g., screening, Day 1, Day 28, etc.); general condition and status remarks by the patient, including any *significant* medical findings; the severity, frequency, duration, and resolution of any reported AE, and the Investigator's assessment as to whether or not the reported AE is study drug-related; changes in concomitant medications or dosages; and a general reference to the procedures completed; and the signature or initials of all physicians making an entry in the medical record (progress notes).

In addition, any contact with the patient via telephone or other means that provides significant clinical information will also be documented in the medical record (progress notes), as described above.

Information from the medical records (progress notes) and other source documents will be promptly transcribed to the appropriate section of the eCRF.

Changes to information in the medical record (progress notes), eCRF, and other source documents will be initialed and dated on the day the change is made by the Investigator or designee. If the reason for the change is not apparent, a brief explanation for the change will be written adjacent to the change.

# 15.3. Source Documents Maintenance

Source documents contain the results of original observations and activities of a clinical investigation. Source documents include, but are not limited to, medical records (progress notes), computer printouts, screening logs and recorded data from automated instruments.

All source documents from this study will be maintained by the Investigator and made available for inspection by authorized persons. The original signed informed consent for each patient shall be filed with records kept by the Investigator and a copy shall be given to the patient.

